corresponds to the fake device. The Engineer will not reveal this information to any source (investigators, subjects, CRO, or Sponsor) until the final study data analysis is complete and the Post-Study Open-Label phase begins.

Once a subject has signed the informed consent form, the Principal Investigator will contact the Sponsor (via email or phone) who will act as the central source for providing sequential subject procedure group assignment.

SUBJECTS

Subject Sample

Subjects will be males and females aged 18 years or older who have diagnosed diabetic peripheral neuropathy with pain persisting over at least the past three months.

Sample size

There will be 64 qualified subjects enrolled in this clinical study:

32 subjects in the active procedure group
32 subjects in the control procedure group

Rationale for sample size

Based on the following parameters established for the purposes of assessing efficacy of the Erchonia® FX-635™ in this clinical study ...:

- Individual subject success criteria defined as a 30% or greater reduction in self-reported Degree of Pain rating on the 0-100 VAS from baseline to study endpoint evaluation.

N.B.: The clinical relevance of a 30% change in VAS score is explained and supported in the STATISTICAL ANALYSIS PLAN section further along in this protocol document.

- Overall study success criteria of at least a 35% difference between the test device group and the placebo group, comparing the proportion of individual successes in each group.
- It is anticipated that about 55% of subjects in the test device group and about 20% of subjects in the placebo group will meet the individual success criteria, and
- intended application of a two-tailed test with an alpha value of 0.05 and Power of 0.8

...the sample size of 29 subjects per group (test group and the control group, separately) has been determined using the following reference calculator:

Hypothesis Testing: Categorical Data - Estimation of Sample Size and Power for Comparing Two Binomial Proportions in Bernard Rosner's *Fundamentals of Biostatistics*.

For the purposes of sample size calculation, it is anticipated that about one-twentieth of subjects overall may withdraw from the study prior to completion for various reasons. Therefore, the following formula is used to determine the final needed starting sample size for each group:

Final sample size = sample size X $1/(1-d)$; where d = # expected dropouts/# subjects enrolled.

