- ✓ *'Other' Medication Use:* The subject will record at the end of each day any medication(s) he or she consumed that day that was different from that reported during Baseline evaluation.
- ✓ *Adverse Events* recording, as applicable.

SUBJECT SATISFACTION WITH FOOT PAIN LEVEL: The subject is asked to rate how satisfied he or she is with the level of foot pain experienced at the relevant evaluation points following completion of the laser administration procedures with the Erchonia® FX-635™, by using the 5-point Likert scale presented below to respond to the following question: "Overall, how satisfied or dissatisfied are you with any change in the pain in your feet following the study procedures with the study laser device?"

- Very Satisfied
- Somewhat Satisfied
- Neither Satisfied nor Dissatisfied
- Not Very Satisfied
- Not at All Satisfied

SUBJECT PERCEIVED GROUP ALLOCATION AND RATIONALE: The subject records whether he or she believes to have received the study procedures with the true or fake Erchonia® FX-635™ and records verbatim his or her reasoning or rationale for this perceived determination.

ASSESSMENT INVESTIGATOR PERCEIVED GROUP ALLOCATION AND RATIONALE: The Assessment Investigator records whether he or she believes the subject to have received the study procedures with the true or fake Erchonia® FX-635™ and records verbatim his or her reasoning or rationale for this perceived determination.

RESCUE PAIN MEDICATION USE: As subjects in this study are those that present with a chronic pain level of 50 or greater on the 0 to 100 VAS pain scale, it is unethical to require subjects in this clinical study to refrain from consuming any and all medication(s) indicated for the relief of pain, particularly for subjects assigned to the placebo group. Therefore, this clinical study will incorporate the use of rescue pain medication, to be taken as needed throughout the subject's participation in the clinical study.

The rescue medication to be used in this study will be over-the-counter Regular Strength Tylenol® tablets. Subjects will be instructed to take a dosage of Tylenol as needed to control any foot pain he or she may be experiencing, ensuring that the directions for use are followed.

Subjects will be instructed to record each time a dosage of the pain medication is taken during the study procedure administration and evaluation phase in the Subject Daily Diary.

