For this group, the following secondary efficacy outcome measure will be evaluated:

- d) Change in VAS rating across and between all study evaluation time points to study endpoint evaluation within and between treatment groups

- e) Changes in scores on the Neuropathic Pain Symptom Inventory (NPSI) across and between all evaluation points to study endpoint evaluation within and between treatment groups
- f) Differences in the use of rescue pain medication between procedure groups across study duration to study endpoint evaluation.

STATISTICAL METHODS

Efficacy analysis will be according to the intent to treat (ITT) principle by last observation carried forward (LOCF).

Intent to Treat: Subjects will be included in the analysis if they were randomized to study procedure group, had a valid baseline visit including the required Low Back Pain VAS recordings; and received the first study procedure administration.

Last observation carried forward: Missing data will be handled by carrying forward the last observation.

Per-protocol analysis will also be performed for the set of all subjects who were randomized to procedure group and completed the study according to the full protocol.

STATISTICAL ANALYSIS

The primary analysis of efficacy will be through the application of:

- 1) **Fisher's exact test** to compare the proportion of success between the test and the control groups, considering that randomization has been diligently conducted and important covariates between the two groups are well balanced.
- 2) **Parametric ANCOVA model** analysis with the mean change from baseline to study endpoint in foot pain ratings on the VAS as the dependent variable, procedure group as the independent variable of interest and baseline average foot pain VAS rating as a covariate. A two-tailed significance level of 5% will be considered to be statistically significant.

Covariates: The following potential covariate baseline variables will be adjusted, as applicable, through application of an ANCOVA analysis for the continuous variables and linear regression analysis for categorical variables.

- ✓ Baseline VAS rating
- ✓ Baseline NPSI total score
- ✓ Duration of foot pain
- ✓ Time since Diabetes diagnosis
- ✓ Insulin dependent versus non-insulin dependent Diabetes
- ✓ Age
- ✓ Gender

Secondary Measures Analysis

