- The secondary measures that are continuous variables will be analyzed through parametric analysis using ANCOVA. A two-way significance level of 5% will be considered to be statistically significant.
- The secondary measures that are categorical will be evaluated through linear regression analysis.

Satisfaction with Study Outcome Ratings: will be tabulated according to category and reported as percentages. Satisfaction levels will be correlated with subject individual study success and recorded changes in foot pain VAS ratings from Baseline to post-procedure evaluations.

BLINDING EFFICACY EVALUATION

Statistical evaluation of blinding efficacy will be performed as follows:

- (i) The percentage of subjects who correctly perceived their procedure group allocation and the percentage of subjects who did not correctly perceive their procedure group allocation will be calculated.
- (ii) The percentage of times the assessment investigator correctly perceived subjects' procedure group allocation and the percentage of times the assessment investigator did not correctly perceive subjects' procedure group allocation will be calculated.
- (iii) The Fischer's Exact categorical analysis technique for comparison of proportion of successes (accurate procedure group allocation determination) between actual active and placebo subject groups will be performed.

It is anticipated that the results of the Fischer's Exact analysis will not be statistically significant; that is, it is anticipated that both subjects assigned to the active procedure group and subjects assigned to the placebo procedure group will demonstrate a high percentage of accuracy of group allocation determination if the study treatment proves efficacious. Similarly, it is anticipated that assessment investigators will demonstrate a high percentage of accuracy of group allocation determination for both subjects assigned to the active procedure group and subjects assigned to the placebo procedure group, if the study treatment proves efficacious. Therefore, it should be noted that lack of a statistically significant Fischer's Exact analysis result will be considered an indicator of study blinding efficacy, providing additional support to study outcome efficacy, particularly if appropriately supported by the reasoning statements, as explained below.

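### Linear regression is named for categorical secondary measures, the covariate-adjusted model is left undefined, and no adjusted or site-stratified analysis is specified for the 30% responder endpoint

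*Combined protocol and SAP*

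**What the plan says.** Three parts of the statistical section bear on this point.

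- **Primary analysis.** Study success rests on the proportion of subjects with a VAS reduction of at least 30%. The Statistical Analysis section compares these proportions by Fisher's exact test, on the premise that randomization has balanced the important covariates. It adds an ANCOVA, but for a different outcome: VAS change, with baseline VAS as covariate.
- **Covariates.** Seven baseline variables (VAS, NPSI total, pain duration, time since diabetes diagnosis, insulin dependence, age, gender) are to be adjusted where applicable. ANCOVA is assigned to the continuous ones and "linear regression analysis for categorical variables" is the other half of the rule. No dependent variable is named. Site is not on the list, although the Randomization section stratifies by it.
- **Secondary measures.** ANCOVA is assigned to continuous measures. For the rest: "The secondary measures that are categorical will be evaluated through linear regression analysis".

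Satisfaction is recorded "by using the 5-point Likert scale presented below", but its own paragraph only tabulates it and correlates it with individual success and VAS change. Blinding guesses have Fisher's test and adverse events a chi-square test. Individual Site Analysis adds results by site and pooled over sites. The statistical sections name no logistic, ordinal or stratified categorical method.

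**The concern.** Linear regression on category codes treats the steps between categories as equal, so for an ordinal outcome the estimate and p-value depend on the scores chosen, and for a nominal outcome the scores have no meaning. A plan that makes it the general rule for categorical measures invites that analysis wherever such a measure is compared between groups.

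The covariate rule raises a different problem. Two analysts could follow it and fit different models: one joint model, two separate models divided by covariate type, or a rule that sorts outcomes rather than covariates. The sentence allows each reading.

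The responder endpoint is where this matters most. The plan states a balance premise and lists covariates, but does not say what is done for the responder proportion if balance is imperfect. Any adjusted responder result would then have to be devised after the data are seen. For a trial meant to support a 510(k) submission, that leaves avoidable room for post hoc choice of model and covariates.

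**Working it through.** **Inputs.** Rationale for sample size gives the rates for individual success ("It is anticipated that about 55% of subjects in the test device group and about 20% of subjects in the placebo group will meet"), error rates ("intended application of a two-tailed test with an alpha value of 0.05 and Power of 0.8") and an evaluable number ("the sample size of 29 subjects per group"). Enrolment is "32 subjects in the active procedure group" with the same number in the control group.

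**1. The plan's own figure.** Pooled formula without continuity correction: n = [1.960·√(2·0.375·0.625) + 0.842·√(0.55·0.45 + 0.20·0.80)]² / 0.35² = (1.342 + 0.537)² / 0.1225 = 28.8, so 29 per group, with power 80.2%. The figure reproduces and does not depend on the models discussed here.

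**2. Which outcomes does the linear-regression rule reach?**

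| Measure | Stated method |
|---|---|
| VAS change, NPSI change | ANCOVA (continuous) |
| Rescue medication use | listed without a unit; the diary records each dose |
| Satisfaction | tabulated and correlated |
| Blinding guesses | Fisher's exact test |
| Adverse events | chi-square test |

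No listed secondary efficacy measure is plainly categorical. The rule would apply if rescue use were reduced to any or none, or if satisfaction were compared between groups. The plan states neither.

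**3. ANCOVA against linear regression for covariates.** On simulated data with a continuous and a dummy-coded binary covariate, the treatment p-value was 0.00486 by both routes, as it must be, since they are the same general linear model. Categorical covariates are handled correctly. Splitting by type is what leaves the model undefined.

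**4. Chance imbalance at this size.** With 32 per arm, the standard error of a standardized baseline difference is √(2/32) = 0.25. If the five continuous listed covariates were independent (an assumption), the chance that at least one differs by more than 0.25 SD is 1 − 0.683⁵ = 0.85. Such imbalance does not invalidate Fisher's test, but it makes a question about adjustment likely.

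**5. What adjustment could change.** Simulation with 3000 replicates and 32 per arm, assuming a prognostic covariate with log-odds ratio 1.0 per SD and one null binary covariate:

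| Analysis of response | Power, about 55% vs 20% | Type I error, 20% vs 20% |
|---|---|---|
| Fisher, unadjusted | 77% | 2.7% |
| Linear regression on 0/1, adjusted | 88% | 5.1% |
| Logistic, adjusted (likelihood ratio) | 89% | 6.4% |

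Exact enumeration gives Fisher power of 78.3% at 32 per arm, in line with the simulation. The linear fit produced at least one fitted probability outside 0 to 1 in about 94% of replicates. The power gap is not all due to the covariate, because the tests run at different actual sizes. The Monte Carlo standard error at 5% is √(0.05·0.95/3000) = 0.4 points, so the logistic 6.4% is a real, mild excess.

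**6. How many terms a responder model can carry.** Expected responders: 32·0.55 + 32·0.20 = 17.6 + 6.4 = 24. Group, site (two sites are listed, so one term) and baseline VAS make 3 terms, or 24/3 = 8 responders per term. Group, site and all seven listed covariates make 9 terms, or 24/9 = 2.7 per term.

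**The case against.** The strongest defence is that nothing decisive is wrong. The primary test is valid under randomization without adjustment, the plan makes covariate adjustment conditional, and the sentence on categorical measures reads like boilerplate with almost nothing to act on. Site-by-site results are also planned. Most of this stands, and it sets the size of the point. It does not supply an adjusted responder model, and separate or pooled site results are not a combined analysis that respects the strata.

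A reader might infer more than the documents support:

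- **That linear regression is wrong for categorical covariates.** It is not: gender and insulin dependence enter as indicators (step 3).
- **That no stated model could adjust a binary endpoint.** Linear regression on a 0/1 outcome adjusts a risk difference and held 5.1% type I error in step 5. The plan simply does not specify it for response.
- **That unequal variances at 55% and 20% distort the analysis.** The variances are 0.2475 and 0.16, a ratio of 1.55, but response is tested by Fisher's test. Even for linear regression with equal arms, the unadjusted standard error is unchanged: √(2·0.20375/32) = √(0.2475/32 + 0.16/32) = 0.113.
- **That satisfaction, responder status at other visits or any/none rescue use will be analysed by linear regression.** Satisfaction has its own descriptive treatment, and the other two are not listed outcomes.

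**Conclusion.** The point holds as a minor gap in specification with three parts. Linear regression is a poor default for categorical outcomes, with small practical reach in this plan. The covariate-adjusted model is undefined, because one model is presented as two. No adjusted or site-stratified analysis is specified for the responder endpoint, although site is the stratification factor and covariates are listed for adjustment.

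The primary Fisher comparison is not invalidated, and the planned sample size is unaffected by this point. The documents give no covariate effect, so the gain from adjustment cannot be derived from them. The figures in step 5 rest on the assumed log-odds ratio of 1.0 per SD, do not include site, and should be read only as showing that the choice of model can matter. For satisfaction, no size can be derived without data.

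**What to change.** Keep Fisher's exact test as the primary analysis of response and amend the SAP text as follows.

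1. Pre-specify one supportive responder analysis: either logistic regression with group, site and baseline VAS, or a Cochran-Mantel-Haenszel test stratified by site. If logistic, hold it to those three terms (step 6) and label it supportive, given the mild type I excess in step 5.
2. Replace the linear-regression rule with logistic regression for any binary secondary measure and proportional-odds regression for any between-group comparison of satisfaction. State the unit in which rescue medication use is analysed.
3. For continuous outcomes, put continuous and categorical covariates in a single ANCOVA, include site, and name the dependent variable.

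The cost is SAP wording only. Site and baseline VAS are already collected, and the sample size, visits and case report forms are unchanged. The changes should be made before unblinding.

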The study endpoint evaluation visit will occur at the test site within ten minutes following completion of the procedure administration phase, after administration of the 12th and final procedure administration with the Erchonia® FX-635™.

The following measures will be recorded at this visit:

- Visual Analog Scale (VAS) Degree of Foot Pain Rating
- Neuropathic Pain Symptom Inventory (NPSI)
- Subject Satisfaction With Foot Pain Level
- Subject Perceived Group Allocation and Rationale
- Assessment Investigator Perceived Group Allocation and Rationale
- Adverse Events Evaluation

TWO WEEKS POST-PROCEDURE EVALUATION: AT HOME

Two weeks following completion of the procedure administration phase, the following measures will be recorded:

- Visual Analog Scale (VAS) Degree of Pain Rating
- Adverse Events Evaluation

FOUR WEEKS POST-PROCEDURE EVALUATION: AT HOME

Four weeks following completion of the procedure administration phase, the following measures will be recorded:

- Visual Analog Scale (VAS) Degree of Pain Rating
- Neuropathic Pain Symptom Inventory (NPSI)
- Subject Satisfaction With Foot Pain Level
- Adverse Events Evaluation

THREE MONTHS POST-PROCEDURE EVALUATION: AT HOME

Three months following completion of the procedure administration phase, the following measures will be recorded:

- Visual Analog Scale (VAS) Degree of Pain Rating
- Neuropathic Pain Symptom Inventory (NPSI)
- Subject Satisfaction With Foot Pain Level
- Adverse Events Evaluation

OPEN-LABEL PLACEBO SUBJECT PROCEDURE ADMINISTRATION PERIOD

Following completion of the 3-month post-procedure administration phase, individual subject blinding will be broken. Subjects who had been randomized to the placebo (sham) procedure group will then be offered participation in an additional 6-week post-study open-label procedure administration period during which time they will knowingly receive the active 6-week 12-procedure administration protocol with the Erchonia® FX-635™ Laser as did the subjects initially assigned to the active test procedure group at the time of study enrollment.

Participation in the 6-week post-study open-label procedure administration period is voluntary for subjects who had been assigned to the placebo (sham) procedure group. Participation in the 6-week post-study open-label procedure administration period will not be offered to subjects who had initially been randomized to the active test laser procedure group.

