The primary efficacy outcome evaluation will be performed on the blinded data attained from subjects who were initially enrolled in either the test or placebo procedure group and will not include active procedure test data attained from placebo subjects who partook in the post-study open-label procedure administration period after blinding was broken.

Subjects meeting Individual Success Criteria

The individual subject success criteria defined as a 30% or greater decrease in self-reported VAS pain rating at study endpoint relative to baseline.

Overall Study Success Criteria

Overall study success criteria defined as at least a 35% difference between procedure groups, comparing the proportion of individual successes in each group. It is anticipated that about 55% of subjects in the test group will meet the individual success criteria and about 20% of subjects in the control group will meet the individual success criteria.

The clinical relevance of a 30% change in VAS score has been well previously established by FDA's Division of Surgical, Orthopedic and Restorative Devices through numerous pre-IDE reviews, the results of said studies that were subsequently used to successfully support various pain-reduction related indications for various Erchonia Corporation light therapy devices under Product Code NHN for the 510(k)s listed below over the past 8 years:

1. K180197: *Erchonia*® FX-635: is indicated for the following two indications:
 - a. as an adjunct to provide relief of minor chronic low back pain of musculoskeletal origin.
 - b. as an adjunct to reducing chronic heel pain arising from plantar fasciitis.
2. K101430; 06/22/10: "The MLS-AC DermaScanner™ is indicated, while using the red diodes, for adjunctive use in providing temporary relief of minor chronic neck and shoulder pain of musculoskeletal origin."
3. K100509; 06/08/10: "The Erchonia THL1 is indicated for use in providing temporary relief of minor chronic neck and shoulder pain of musculoskeletal origin."
4. K072206; 04/24/08: "The Erchonia EML Laser is indicated for the temporary reduction in post -surgery pain at 24 hours after surgery following breast augmentation surgery."

5. K050672; 06/02/05: "The Erchonia EVRL Laser is generally indicated while using the red diode for adjunctive use in providing temporary relief of minor chronic neck and shoulder pain of musculoskeletal origin."

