Positive blinding efficacy will be supported by comments provided to support perceived group allocation that pertain to the determination being made based on treatment efficacy or lack thereof; e.g.: 'My foot pain is much less than it used to be, so I believe I got the real treatment' or 'My foot pain hasn't really changed, so I believe I got the fake treatment.'

Blinding will be determined to have failed if comments provided to support perceived group allocation pertain to factors such as sensation/visual clues (e.g. I saw/didn't see a light go on the laser, etc.) or other factors that pertain to blinding having been compromised such as 'I overheard the doctor saying I wasn't getting the real treatment.'

SAFETY ANALYSES

Safety analyses will be based on all subjects who were randomized to test or placebo procedure group. Safety will be assessed by evaluating and comparing frequency and incidence of observed and/or reported adverse events between test and placebo procedure groups related to administration of the Erchonia® FX-635™ laser procedures. A chi-square test with a continuity correction will be performed to compare the percentage of subjects who experienced adverse events between test and placebo procedure group subjects.

INDIVIDUAL SITE ANALYSIS

Analysis of results will be performed by individual test site and pooled across test sites. Application of a balanced test-control group study design incorporating a varied block by test site randomization procedure will contribute to statistical justification of pooling data across the different test sites.

INFORMED CONSENT

- Informed consent will be an agreement between the individual investigator and each subject, having the capacity to understand and make an informed decision. Consent will be obtained prior to each potential subject's participation in this clinical study.
- Each subject participating in this clinical study will be made aware of the fact that his or her participation involves research and the intent of the research, the expected duration of his or her participation and a description of the procedures that will be followed.
- Each subject will be made aware of the reasonably expected benefits he or she might receive, as well as any risks or potential discomfort that are involved.
- Each subject will also be made aware of alternative treatments available to him or her.

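### The planned blinding test compares guess accuracy between arms, so a non-significant result shows neither an intact blind nor efficacy

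*Combined protocol and SAP*

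**What the plan says.** The BLINDING EFFICACY EVALUATION section has three numerical items and a rule about comments.

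- Item (i) reports "The percentage of subjects who correctly perceived their procedure group allocation" and the percentage who did not. Item (ii) does the same for the assessment investigator. Neither gives a reference value or specifies a split by arm.
- Item (iii) is a Fisher's exact test for "comparison of proportion of successes (accurate procedure group allocation determination) between actual active and placebo subject groups". No alpha is stated.
- The plan expects a non-significant result because subjects in both arms "will demonstrate a high percentage of accuracy of group allocation determination if the study treatment proves efficacious". It then says that lack of significance "will be considered an indicator of study blinding efficacy, providing additional support to study outcome efficacy, particularly if appropriately supported by the reasoning statements".
- The comment rule reads: "Blinding will be determined to have failed if comments provided to support perceived group allocation pertain to factors such as sensation/visual clues". Reasons based on pain relief, or the lack of it, count in favour of blinding.

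Subjects record a guess and their reason. So does the assessor, under STUDY TEST BATTERY: "The Assessment Investigator records whether he or she believes the subject to have received the study procedures with the true or fake" device. Both are recorded at the study endpoint evaluation, "within ten minutes following completion of the procedure administration phase, after administration of the 12th and final procedure administration".

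**The concern.** If the blind holds, the share of subjects saying 'true' should not depend on the device they received, apart from any effect of treatment that they notice. Item (iii) does not examine this. It examines whether accuracy is the same in the two arms, which is equally so when nobody knows the allocation and when everybody does.

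The plan nevertheless credits non-significance twice, once as a sign of blinding and once as support for efficacy. The word introducing the reasoning statements makes them a reinforcement, not a condition.

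The primary outcome is a self-reported pain rating intended to support a 510(k) submission, so a reader judging a positive result will look at this check. As written, the plan commits in advance to citing a result that does not bear on the question.

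**Working it through.** **Inputs.** 32 per arm enrolled and 29 per arm expected to remain at the end of the trial (Rationale for sample size). Because follow-up continues after the endpoint visit, 29 is a low figure for that visit. Anticipated responder rates are 55% active and 20% placebo (Overall Study Success Criteria). Two-sided 0.05 is assumed for item (iii).

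**The plan's own figure.** The blinding section states no number, so the check starts from the sample size. With pooled variance and mean proportion 0.375, n = [1.96·√(2·0.375·0.625) + 0.8416·√(0.55·0.45 + 0.20·0.80)]² / 0.35² = (1.342 + 0.537)² / 0.1225 ≈ 28.8, which rounds up to 29. Then 29/0.917 = 31.62, which rounds up to 32. Both figures reproduce.

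**What each test compares.** Let a = P(says 'true' | active) and b = P(says 'true' | placebo). Accuracy is a in the active arm and 1 − b in the placebo arm.

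- Null of item (iii): a = 1 − b.
- Null of no association between guess and arm: a = b.

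Both nulls hold together only when a = b = 0.5.

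**Single tables, 32 per arm (Fisher, two-sided).**

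| Correct, active v placebo | Item (iii) p | Guess by arm p |
|---|---|---|
| 32/32 v 32/32 | 1.0 | 1.1e-18 |
| 29/32 v 29/32 | 1.0 | 2.7e-11 |
| 16/32 v 16/32 | 1.0 | 1.0 |

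**How often item (iii) is non-significant when accuracy is equal in both arms (assumed).** Exact enumeration of two binomials, rejecting at p ≤ 0.05:

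| Accuracy in both arms | 32 per arm | 29 per arm |
|---|---|---|
| 50% | 96.7% | 97.5% |
| 70% | 97.2% | 97.5% |
| 80% | 97.6% | 97.9% |
| 90% | 98.9% | 99.1% |

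**The plan's own expected case.** Suppose subjects say 'true' exactly when they meet the 30% criterion (assumed), at 55% and 20%, with no leak. Accuracy is then 55% active and 1 − 0.20 = 80% placebo, or (55 + 80)/2 = 67.5% overall.

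- Item (iii) is significant 48% of the time at 32 per arm (42% at 29), so the anticipated non-significance is far from assured even here.
- Guess by arm is significant 78% of the time (71%).
- The exact 95% interval for overall percent correct lies above 50% in 77% of trials (78%).
- If 90% of subjects guess this way and the rest the opposite (assumed), the rates saying 'true' are 54% v 26% and guess by arm is significant 56% of the time (48%). If 80% do, the rates are 53% v 32% and the figure is 33% (26%).

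**Intact blind with a shared lean towards 'true' (assumed).** If 60% of both arms say 'true', item (iii) is significant 30% of the time (24% at 29). If 70% do, the figure is 88% (81%). Guess by arm stays at 2% to 3%.

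**The case against.** The strongest reply is that item (iii) is only one indicator among several. Percent correct is reported, and the comment rule can declare the blind failed from stated reasons even at p = 1.0. That is true, and it protects the section as a whole against a leak that people admit to. It does not make a non-significant item (iii) informative, and the plan credits that result whether or not the reasons add to it.

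Second, the 97% to 99% figures assume equal accuracy, which is the test's own null. That also stands: they are conditional, and equal accuracy is not what the 55%/20% design implies. Their purpose is to show that the indicator is met about as often at chance as at 90% accuracy.

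Third, guess by arm cannot separate a leak from a real effect when guesses follow the 12th procedure. This is correct and limits the replacement, as the 78% above shows. It counts equally against the plan's rule, since guesses drawn from pain response are not independent support for that response. An earlier guess would help but would add data collection, so it is not requested here.

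Fourth, the assessor guesses repeatedly, so those guesses may not be independent. With randomisation stratified by site this should matter little for a comparison between arms.

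Last, a significant item (iii) has no stated consequence, so the shared-lean figures show only that an intact blind could lose a supportive indicator.

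**Conclusion.** The concern holds. Item (iii) tests equality of accuracy, and its non-significance supports neither blinding nor efficacy. Given equal accuracy, it is non-significant about 97% of the time at chance and 99% at 90% accuracy, at either sample size to the nearest point or so. This rests on an assumed two-sided 0.05 and assumed accuracies, because the section states neither; the single-table p-values of 1.0 need no assumed accuracy or alpha.

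High accuracy at the endpoint is not itself evidence of a leak, and nothing here suggests that the blind will fail. The consequence is confined to interpretation: the success criteria, the primary test and its error rate do not change. The plan should be corrected on this point, but the trial does not depend on it.

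**What to change.** 1. Delete the sentence that treats lack of significance as an indicator of blinding and as support for efficacy.
2. Replace item (iii) with guess (true or fake) by actual arm, or an arm-specific blinding index, with a 95% confidence interval, separately for subjects and for the assessment investigator.
3. Show percent correct by arm with its interval, beside 50% as a reference and not as a pass mark.
4. State that an association at the endpoint is not by itself evidence of a leak, that it is to be read with the recorded reasons from subjects and assessor, and that neither is evidence of efficacy.

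To illustrate the output at 29 per arm: 16/29 v 6/29 saying 'true' is a difference of 34 points (Newcombe 95% CI 10 to 54), and 15/29 v 14/29 is 3 points (−21 to 27).

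The cost is SAP wording. Guesses and verbatim reasons are already scheduled at the endpoint visit, so visits, sample size and primary analysis are unchanged.
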